Study Hypothesis:	TTFields has been shown to be safe and efficacious in large trials with glioblastoma patients in combination with adjuvant temozolomide but concurrent use together with trimodal therapy has not been examined in clinical trials. Our primary hypothesis is that the TTFields treatment, if initiated concurrently along with radiation and temozolomide therapy, would not significantly alter the safety profile. Secondarily, continuation of early initiated TTF along with adjuvant temozolomide treatment as per the standard of care would increase progression and overall survival. The primary hypothesis is safety and will be tested directly in this trial, but the secondary hypothesis would be assessed only with preliminary observations and need validation in a larger trial that is statistically powered for that investigation.
Sample Size:	30 patients total, 6 included in the first safety lead-in and 15 in the second safety lead-in.
Study Population:	Patients with newly diagnosed histologically confirmed glioblastoma after maximally safe resection, with MGMT methylation status in process, are eligible for enrollment.
Primary Endpoint:	The primary endpoint is safety and tolerability of the combined use of TTFields added to standard chemoradiation and TMZ.
Secondary Endpoints:	Our secondary endpoints will be progression-free and overall survival, imaging response by RANO criteria, and duration and compliance of TTF use.

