In the event of a dose-limiting toxicity, the subject will be discontinued from treatment and followed for toxicity assessment and management and a joint decision will be made by the investigator and sponsor whether to adjust the dose or schedule for other subjects or permanently close the study for safety. In the event that more than 33% of subjects experience a DLT, the study cannot continue unless a modification is made to the level of the particular treatment to which that adverse event is definitely attributable. As preliminary safety stops, the study will include two safety lead-ins receiving TTFields with concurrent chemoradiation. These initial 6 and then 15 subjects will undergo interim analyses after completion of chemoradiation to determine if the expanded cohorts should be permitted enrollment as planned or if a dose reduction in TTFields of 50% of the scheduled use is warranted for safety.

Subjects will continue to receive study treatment until confirmed tumor progression, unacceptable toxicity, or other discontinuation criteria as described; subjects MUST discontinue investigational product (and non-investigational product at the discretion of the investigator) if they meet criteria for removal from study therapy as referenced in that section.

Toxicity related to TTFields treatment: Treatment-related adverse events (TRAEs) and severe treatment-related adverse events (STRAEs) will be assessed in the following ways.

- Patients will be evaluated by a neuro-oncologist or radiation oncologist for potential skin toxicity from TTFields therapy. Routine skin care recommendations will be provided, including use clobetasol cream prior to electrode placement and adjusting array placement to avoid continued site irritation. If there are concerns by investigator, the subject will be referred to a dermatologist for specialized evaluation. Neurological and general physical evaluations as well as laboratory assessments will also be conducted by a neuro-oncologist or radiation oncologist to identify other potential toxicities.
- In addition to clinic visits and interventions, Patients will also be supported by a technician from Novocure for device troubleshooting and compliance checks.
- All other adverse effects, either mild, or serious, will be triaged by a physician in coordination with the primary investigators of the study.

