8. STATISTICAL CONSIDERATIONS

Interim analyses of the first and second safety lead-in cohorts will be performed using data collected from the beginning of the study to eight weeks following trimodal therapy for each patient. Patient characteristics will be summarized using means, standard deviations, medians, interquartile ranges, counts, or percentages, as appropriate. Primary endpoints will be summarized using counts and percentages of patients who experienced a treatment-related adverse event, treatment-related serious adverse event, or DLT for safety and stopping rules.

In the second interim analysis, the percentage of patients with inconclusive MGMT methylation status will also be summarized. Patients with inconclusive MGMT methylation status will be removed from the final study analysis, so we will use this percentage to assess the number of additional patients that need to be recruited to meet our sample size requirement of 30 patients. For example, if 2 out of 15 patients have an inconclusive MGMT methylation status at this stage, we will recruit 4 additional patients to meet the sample size requirement.

Using the intention-to-treat approach, the final analyses will be performed on all patients having received at least one day of use from the study device. Patients with an inconclusive MGMT methylation status will be excluded. Patient characteristics will be summarized using

means, standard deviations, medians, interquartile ranges, counts, or percentages, as appropriate.

Primary endpoints will be summarized using counts and percentages of patients who experienced a treatment-related adverse event, treatment-related serious adverse event, or DLT will be reported overall and by event type following trimodal treatment and 8 weeks thereafter to capture any later appearing toxicities. A subgroup evaluation by MGMT methylation status (methylated vs unmethylated) will also be performed.

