Kaplan Meier survival analyses will be used to analyze the following secondary endpoints: 1) progression-free survival at 6 months and 2 years, 2) median time-to-death and overall survival at 2 years and 3) duration of TTF use. Log rank tests may be used in Kaplan Meier analyses to test for differences in survival curves amongst known prognostic factors such as age, duration and compliance of TTF use, KPS, extent of resection, IDH mutation status, and MGMT methylation status. The objective response by modified RANO criteria will be summarized with counts and percentages following trimodal treatment and at 2 years. The rate of TTFields compliance will be reported as the percentage of patients who used TTFields at least 75% of the minimum recommended usage of 18 hours a day on average, as assessed monthly.

The intention-to-treat analyses may be supplemented by per-protocol analyses, if the percentage of patients who did not follow standard of care recommendations as outlined for adjuvant and maintenance therapy following trimodal treatment is high.

Power Calculation

As we are expecting that patients will be more susceptible to skin irritation with concurrent therapy than with successive therapy, we focus on severe skin irritation as our endpoint for this power calculation. We expect 5% of patients will experience severe skin irritation based on a 2% rate in the Stupp et al. 2015 study (EF-14)²⁴ which used TTField therapy following initial chemoradiation treatment. Assuming a sample size of 30 patients of whom 5% experience severe skin irritation, we can say with 95% confidence that the true percentage of patients with severe skin irritation is no lower than 2% and no higher than 21% based on a one-sample binomial proportion. Outside of severe skin toxicity, the rate of any adverse event is not expected to differ significantly from that established by the EF-14 trial.

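### The synopsis promises a direct test of unchanged safety, but Section 8 plans only counts and percentages, and 30 patients without a like-for-like reference can support estimation only

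*Combined protocol and SAP*

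**What the plan says.** The Study Hypothesis entry in Section 1 states that adding TTFields to radiation and temozolomide "would not significantly alter the safety profile". It continues: "The primary hypothesis is safety and will be tested directly in this trial". The same sentence gives the efficacy hypothesis a lower status: preliminary observation only, to be validated in a larger, powered trial.

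Section 8 sets out the final primary analysis: "Primary endpoints will be summarized using counts and percentages of patients who experienced a treatment-related adverse event", a treatment-related serious event or a DLT. Results are given overall, by event type and by MGMT status. The only tests Section 8 names are optional log rank tests for secondary endpoints.

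The Power Calculation in Section 8 starts from the opposite expectation for skin: "As we are expecting that patients will be more susceptible to skin irritation with concurrent therapy than with successive therapy". It sets the figures as follows: "We expect 5% of patients will experience severe skin irritation based on a 2% rate" in EF-14. From 30 patients it derives a 95% interval of 2% to 21%. For everything except severe skin toxicity it says that "the rate of any adverse event is not expected to differ significantly from that established by the EF-14 trial".

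Section 4 notes that EF-14 patients did not begin TTFields until radiation was over. Section 6 sets the primary toxicity window as trimodal therapy plus the following 8 weeks.

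**The concern.** The synopsis makes an inferential claim and sets it deliberately above the merely observational status of the efficacy hypothesis. A hypothesis of no significant change needs three things before it can be tested: a reference rate, a definition of what counts as change, and a rule applied to the final data. Section 8 supplies none of them for the primary endpoints.

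This affects what the trial may conclude. With 30 patients and no margin, failing to see a significant change is a likely result even if severe toxicity has risen severalfold. Section 5 presents the trial as the foundation for a large phase II study. An unremarkable toxicity table could then be reported as confirming a directly tested hypothesis of unchanged safety, for a combination that Section 4 says no clinical trial had yet used.

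**Working it through.** **Inputs.** n = 30 (Sections 1 and 8). Reference rate 2% from EF-14 and expected rate 5%, both for severe skin irritation (Power Calculation). The plan gives no alpha, sidedness, null value or power for a primary test, so those used below are assumptions.

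**Step 1: the plan's own figure.** 5% of 30 is 1.5 events. Rounded up to 2 of 30, with p = 2/30 = 0.0667 and z = 1.96, the Wilson score interval is

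- centre: (p + z²/2n)/(1 + z²/n) = (0.0667 + 0.0640)/1.1281 = 0.1159
- half-width: z·√(p(1−p)/n + z²/4n²)/(1 + z²/n) = 0.0974
- limits: 1.85% and 21.3%

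This reproduces the stated 2% to 21%. It is a planning calculation for an assumed result and does not commit the analysis to an interval around the observed rates. It rests on 6.7% rather than exactly 5%.

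**Step 2: what a test against 2% could do.** Take an exact binomial test that rejects for a high count.

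- Size at 3 or more events: 1 − [0.98³⁰ + 30(0.02)(0.98)²⁹ + 435(0.02)²(0.98)²⁸] = 1 − (0.5455 + 0.3340 + 0.0988) = 2.2%.
- Rejecting at 2 or more would have size 12.1%. The critical value is therefore 3, at one-sided 5% and at one-sided 2.5% alike.
- Power at a true 5%: 1 − [0.95³⁰ + 30(0.05)(0.95)²⁹ + 435(0.05)²(0.95)²⁸] = 1 − (0.2146 + 0.3389 + 0.2586) = 18.8%.
- Power at a true 10%: 58.9%. At 15%: 84.9%.

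The assumed test would thus miss the plan's own expected rise 100 − 18.8 = 81.2% of the time, and a fivefold rise 41.1% of the time. If 24 to 34 patients were analysed, the one-sided 5% critical value stays at 3 and power at 5% runs from 11.6% to 24.1%. For scale only, 80% power for 2% against 5% needs 226 patients at one-sided 5%, or 272 at one-sided 2.5%.

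**Step 3: what reassuring data would show.** Two-sided exact (Clopper-Pearson) 95% limits for n = 30:

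| Events | Lower | Upper |
|---|---|---|
| 0 | 0% | 11.6% |
| 1 | 0.1% | 17.2% |
| 2 | 0.8% | 22.1% |
| 3 | 2.1% | 26.5% |

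The first upper limit is 1 − 0.025^(1/30) = 0.1157. Even with no events, a rate 11.6/2 = 5.8 times the EF-14 figure is not excluded.

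**Step 4: the reference.** EF-14 exposure to TTFields begins after radiation; the primary window here includes the whole radiation course. Section 6 (Treatment Modalities) lists skin reactions, headache, fatigue and seizure among the acute effects of radiation itself. A difference from EF-14, or its absence, cannot be attributed to concurrent TTFields.

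**The case against.** The strongest reply is that this is a single-arm phase I pilot, for which descriptive safety reporting is normal. Section 6 (Primary Study Endpoints) already speaks of identifying rates, and no enrolment or stopping decision depends on the synopsis sentence. That stands. It limits the severity, and it supports changing the claim rather than the design.

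A reader might also infer four stronger things, which the documents do not support.

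- *Section 8 has no interval and the plan has no decision limits.* Section 8 contains the 2% to 21% planning interval and refers to stopping rules. Section 6 (Safety Lead-ins) gives DLT limits of 2 or more of 6 and 5 or more of 15. Section 7a adds "In the event that more than 33% of subjects experience a DLT, the study cannot continue" unless the treatment level is modified. These limits govern whether the trial continues; none is a criterion for the final analysis.
- *The design has a stated power that is wrong.* The plan states no power and sizes the trial by precision. The 81.2% belongs to an assumed test with 2% treated as fixed, ignoring sampling error in EF-14.
- *The expected rise to 5% flatly contradicts the hypothesis.* The hypothesis says not significantly altered, and the Power Calculation exempts severe skin toxicity from its expectation of similarity. The two sit badly together, but this is loose wording.
- *The final DLT rate should be judged by whether a confidence limit lies below 33%.* The 33% is a trigger on the observed proportion during conduct. Applying it to a confidence limit would create a new criterion whose outcome depends on sidedness: for 5 of 30 the upper limit is 31.9% one-sided and 34.7% two-sided.

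Nor do the documents supply a better external reference. For the cited randomised trial of radiotherapy plus temozolomide they give survival and progression figures but no toxicity rates for the radiation phase.

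**Conclusion.** The point holds as a mismatch between claim and analysis. The synopsis promises a direct test. Section 8 provides no hypothesis test, margin, planned interval for the observed primary rates or final criterion, and the one named reference does not cover the radiation phase.

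The power figures illustrate why 30 patients cannot carry that claim. They assume independent patients, a fixed 2% reference and conventional one-sided levels. The 11.6% upper limit at 0 of 30 does not depend on the 2% reference or on choosing a test, and by itself shows that an unchanged profile cannot be established.

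Estimation in 30 patients remains a reasonable aim. Severity: should fix.

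**What to change.** 1. **Section 1, Study Hypothesis.** Replace the statement that safety will be tested directly with an aim to estimate the rates of treatment-related adverse events, treatment-related serious adverse events and DLTs in the primary window. State that the trial cannot establish that the safety profile is unchanged.
2. **Section 8, final analysis.** Report each of these rates, and the rate of severe skin toxicity, with a two-sided exact (Clopper-Pearson) 95% interval.
3. **Section 8, Power Calculation.** State that EF-14 rates are descriptive context only and do not cover the radiation phase.

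No new acceptance limit and no further external comparator are needed. The cost is a protocol and SAP wording change, one added column of intervals, and a less favourable stated claim. It needs no extra patients, visits or data.

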2. IDENTIFICATION AND DESCRIPTION OF THE INVESTIGATIONAL DEVICE

a) Description of the Investigational Device and its Intended Purpose

Optune™ is intended as a treatment for adult patients (22 years of age or older) with histologically-confirmed glioblastoma multiforme (GBM).

Optune™ with temozolomide is indicated for treatment of adult patients with newly diagnosed, supratentorial glioblastoma following maximal debulking surgery and completion of radiation therapy together with concomitant standard of care chemotherapy.

For the treatment of recurrent GBM, Optune™ is indicated following histologically or radiologically-confirmed recurrence in the supratentorial region of the brain after receiving chemotherapy. The device is intended to be used as a monotherapy, and is intended as an alternative standard medical therapy for GBM after surgical and radiation options have been exhausted.

Under this clinical trial, Optune™ is also intended to be used for the treatment of newly diagnosed glioblastoma following maximal debulking surgery, however, the treatment will be initiated concurrent with (not after completion of) radiation therapy along with temozolomide.

The device is a portable, battery operated system which delivers TTFields to the patient by means of insulated Transducer Arrays (INE transducer arrays). Optune™ produces electric forces intended to disrupt cancer cell division.

b) Details Concerning the Manufacturer of the Investigational Device

The Optune™ System is manufactured by Novocure Ltd., [name]. Novocure Ltd. is an EN ISO 13485 approved and 21CFR820 compliant medical device company developing electric field based therapy for cancer patients. Novocure's headquarters are located in Israel. Novocure GmbH is the EN ISO 13485 approved and 21CFR820 compliant Novocure Ltd global distribution center. Novocure GmbH is based in Switzerland.

c) System Parts and Their Identification

The Optune™ System is composed of several parts, which are shown in the picture below.

1 Power supply

2 Charger

3 Insulated transducer arrays

4 Device carrying bag

5 Optune™ electric field generator (the device)

6 Portable battery

7 Connection cable & box

d) Traceability

All parts of the Optune™ System are identified by a unique and personal serial number. Transducer arrays are identified by lot number. Novocure maintains traceability of all parts through paper documentation and SAP ERP:

[figure not shown]
Steps	Traceability ensured by
Manufacturing	EN ISO 13485 Vendor Quality System
Receiving	SOP-USOC-002 Incoming Inspection and SAP ERP
Storage	SOP-USOC-004 Stockroom and SAP ERP
Shipping	SOP-USOC-003 Shipping- Final release and SAP ERP
Use	SAP ERP

e) Intended Purpose of the Investigational Device in the Proposed Clinical Trial

The Optune™ System is intended for the treatment of newly diagnosed glioblastoma following maximal debulking surgery concurrent with chemoradiation therapy.

f) Materials That Will Be in Contact with Tissues

The INE transducer arrays are applied directly to the skin.

These arrays are sterile single use devices and incorporate the following:

	Part name	Functions
1	Cover tape	Provides adhesion of the array to patients' skin
2	INE transducer array	The array delivers the treatment to the patient and measures the temperature
3	Conductive gel layers and ceramic discs (beneath)	Gel: Ensures electric contact between the transducer array and the skin Ceramic disc: Used for the TTFields transmission
4	Mid-pads	Mechanically stabilizes the gel over the array
5	Overlapping liner	Covers the gel and the cover tape
6	Applied part cable with black connector or white connector	Connects the transducer array to the connection box

g) Training Procedures Involved in the Use of the Investigational Device

The Optune™ System is easy to use and a simple training by the Device Support Specialist (DSS) is sufficient for patients and the study team to apply the investigational device according to its intended use. No specific medical/surgical procedures are needed for the use of the investigational device.

3. SCIENTIFIC BACKGROUND RELEVANT FOR THE DESIGN OF THE CLINICAL TRIAL

a) Glioblastoma multiforme (GBM)

GBM, a malignant form of astrocytoma, is the most common of all malignant primary brain and CNS tumors. The incidence rate of GBM is 3.2 per 100,000 population. Incidence increases steadily above 45 years of age with 12,120 cases predicted in 2016 in the US. GBM is the most lethal brain tumor. Despite numerous attempts to improve the outcome of patients with GBM, only one-third of patients survive for one year and the 5-year survival rate is only 5.1 %¹.

Before the introduction of TTFields, treatment of newly diagnosed GBM was based on surgical resection with or without Gliadel Wafer implantation, radiotherapy, and temozolomide. Patients with newly diagnosed GBM who were treated with maximal surgical resection, 60 Gy radiotherapy together with temozolomide, followed by maintenance temozolomide for 6 months, had a median survival of 14.6 months².

Each of these treatments is briefly described below:

1. Surgical resection - Treatment of patients with GBM usually begins with resection or biopsy, with maximal safe debulking of the tumor as the main goal because curative resection is exceedingly rare.
2. Radiation therapy - Post-surgical radiation therapy has been shown to improve survival, though even with maximal treatment, survival after RT alone is still limited to about one year².
3. Temozolomide – Adjuvant temozolomide and radiation therapy following surgery has been shown to improve survival by about 20%. According to the temozolomide package insert adjuvant temozolomide treatment delays disease progression (from 5 to 6.9 months) and improves overall survival (from 12.1 to 14.6 months)².

Unfortunately, nearly all glioblastoma cases recur. At recurrence the management depends on the extent of the disease and patient's performance status. Treatment options include re-resection with or without wafer placement in the surgical bed, systemic chemotherapy, re-irradiation and TTFields.

b) Tumor Treating Fields (TTFields) Overview

TTFields are a non-invasive, regional antimitotic treatment modality with which has been approved for the treatment of recurrent and newly diagnosed GBM by the Food and Drug Administration (FDA) in the United States. The instructions for use of Optune™ can be found at: https://www.optune.com/Content/pdfs/Optune_IFU_8.5x11.pdf

TTFields act by delivering low intensity (1-3 V/cm), intermediate frequency (100-300 kHz) alternating electric fields to the tumor using non-invasive transducer arrays placed on the skin around the region of the body containing the tumor. TTFields act during mitosis by disrupting the formation of the mitotic spindle during metaphase, by impeding the normal midline

localization of septin complex in cells which have entered anaphase, inducing violent cytoplasmic blebbing and mitotic failure, and by dielectrophoretic dislocation of intracellular constituents during cytokinesis, resulting in apoptosis³⁻⁷. The efficacy of TTFields is frequency dependent on specific cell types. The anti-mitotic effect of TTFields has been shown in multiple cell lines when the appropriate frequency was utilized. This includes but not limited to the following tumor models: glioblastoma at 200 kHz⁷, NSCLC at 150kHz⁸; breast carcinoma at 120kHz⁹; melanoma at 100kHz¹⁰.

The effect of TTFields is directional, i.e., TTFields are most effective when applied in the direction of the division axis of the dividing cell^{3,7}. In order to increase the efficacy of TTFields, two sequential field directions can be applied to tumors by using two perpendicular pairs of transducer arrays.

c) Preclinical Results with TTFields

TTFields and Radiation Therapy

TTFields have demonstrated significant activity in *in vitro* and *in vivo* glioma preclinical models both as a single modality treatment and in combination with irradiation. Radiation therapy (RT) has significantly greater efficacy when combined with TTFields according to an evaluation that compared the surviving fraction of U-87 MG and U-118 MG cultures glioma cell cultures¹¹. The combination therapy was found to be most effective when TTFields were applied immediately after exposure to RT. Aberrant DNA damage repair and extended retention of γH2AX and Rad51 nuclear foci in cells 24 hours after exposure to both modalities. Combining TTFields treatment and IR led to a further decrease in the surviving fraction for all tested radiation doses in both cell lines. Additionally, TTFields delayed DNA damage repair following irradiation induced damage^{11, 19, 20}. This was achieved through inhibition of double stand DNA damage repair by homologous recombination.

Investigations using an ion chamber connected to a unidos dosimeter demonstrated that the TTFields transducer arrays absorb only a small fraction of the irradiation energy, but lead to a dramatic increase in the energy directly below the ceramic arrays that could potentially abolish the "skin sparing" effect¹². Further experiments showed that no additional skin adverse events were observed when single irradiation dose of 10 Gy was applied to the rat head through the transducers. Skin screening revealed that irradiation through the ceramic arrays did not lead to adverse skin reactions when rats were irradiated with 2 Gy, five times a week for two weeks through ceramic arrays placed on the rat's dorsal skin.

Effects of the tumor suppressor gene p53 on TTFields

The surviving fractions of glioma cell lines expressing either wild-type p53 (A-172 and U-87 MG) or mutant p53 (U-118 MG and F-98 rat glioma) demonstrated that the application of TTFields led to a significant reduction in cell count and clonogenic potential as compared to untreated cells in both p53 wt and p53 mutant cell lines¹³. Analysis of Annexin V and Propidium Iodide expression revealed that TTFields-induced apoptosis is independent of p53 status. Caspase activity was increased in wt p53 cells following TTFields application, however no increase was

observed in mutant p53 cells. This demonstrates that TTFields exposure induces apoptosis by both p53-dependent and p53-independent pathways.

TTFields effects on cell migration

Application of TTFields in-vitro led to a significant reduction in both migratory and invasive phenotype in multiple glioma cell lines¹⁴. Specifically, cell migration velocity, as assessed by the wound healing assay, was significantly reduced in U-87 MG (31%, P<0.001), and in A-172 (27%, P<0.001) compared with untreated control cells. The number of invading cells, as assessed by the modified Boyden chamber assay, was reduced in U-87 MG (54%, P<0.05), A-172 (68%, P<0.05), LN-229 (38%, P<0.01) and in LN-18 (55%, P<0.05) compared with untreated control cells. These results suggest that human glioma cell motility is impaired by exposure to TTFields.

d) Clinical Results with Optune™ in Glioblastoma

Based on promising pilot data in both recurrent and newly diagnosed glioblastoma, a phase III trial was conducted in the United States and Europe to test the safety and efficacy of 200 kHz TTFields alone versus active chemotherapy in patients with recurrent glioblastoma¹⁵. The primary endpoint was overall survival. Patients (median age 54 years (range 23-80), Karnofsky performance status 80% (range 50-100)) were randomized to 200 kHz TTFields alone (n=120) or active chemotherapy control (n=117). The treatment of control arm was based on physician-selected active chemotherapy that predominantly included bevacizumab based regimens, irinotecan or nitrosurea. The median number of prior treatments was 2 (range 1-6).

Median overall survival was 6.6 vs. 6.0 months (hazard ratio 0.86 [95% CI 0.66-1.12]; p=0.27), 1-year survival rate was 20% and 20% and progression-free survival rate at 6 months was 21.4% and 15.1% (p=0.13), respectively in TTFields versus chemotherapy treated patients. Responses were more frequent in the TTFields arm (14% vs. 9.6%, p=0.19). The most common TTFields-related adverse event was mild (14%) to moderate (2%) skin irritation beneath the transducer arrays, which was again expected with use of the transducer arrays. These adverse events were effectively treated with topical hydrocortisone. Patients receiving chemotherapy had significantly more gastrointestinal, hematological and infectious complications. Quality of life analyses favored TTFields in most domains. Specifically, cognitive and emotional function were reported to be much better in the TTFields treated patients than with chemotherapy.

The results of this phase III trial demonstrated comparable efficacy with this chemotherapy-free treatment (200 kHz TTFields) to chemotherapy (including bevacizumab) in recurrent glioblastoma with a more favorable safety profile and quality of life and supported FDA approval of TTFields in recurrent glioblastoma in 2011 and a CE mark in Europe.

Registry data from 457 recurrent GBM patients who started Optune™ prescribed by the treating physician in the US between October 2011 and November 2013 showed an even higher median overall survival of 9.6 months, with baseline characteristics similar to those of patients treated under the pivotal clinical trial¹⁷. The 2-year survival rate in this population was 30% (compared to 9% in Optune™-treated patients on the clinical trial). Compliance was a clear predictor of survival on Optune™, and patients treated with the device for at least 18 hours per

day had significantly longer survival time. No new safety signals have been detected in this registry dataset and the only common adverse event related to Optune™ was dermatitis. Based on this clinical data in recurrent GBM and a pilot trial in newly diagnosed GBM with Optune™ in combination with temozolomide that demonstrated favorable safety profile and promising efficacy, an international phase III trial in newly diagnosed GBM, evaluating the role of Optune™ in combination with temozolomide maintenance after surgery and chemoradiation versus temozolomide alone was conducted¹⁴. An interim analysis included 210 patients randomized to TTFields plus temozolomide and 105 randomized to temozolomide alone, and was conducted at a median follow-up of 38 months (range, 18-60 months). Median progression-free survival in the intent-to-treat population was 7.1 months (95% CI, 5.9-8.2 months) in the Optune™ plus temozolomide group and 4.0 months (95% CI, 3.3-5.2 months) in the temozolomide alone group (hazard ratio [HR], 0.62 [98.7% CI, 0.43-0.89]; P = .001). Median overall survival in the per-protocol population was 20.5 months (95% CI, 16.7-25.0 months) in the Optune™ plus temozolomide group (n = 196) and 15.6 months (95% CI, 13.3-19.1 months) in the temozolomide alone group (n = 84) (HR, 0.64 [99.4% CI, 0.42-0.98]; P = .004). Quality of life and gross cognitive function were also comparable in the 2 arms¹⁸.

Based on the data submitted to FDA from this newly diagnosed GBM study, FDA approved Optune™ in combination with temozolomide for the treatment of adult patients with newly diagnosed GBM on October 5, 2015. In the US, Optune™ with temozolomide is indicated for the treatment of adult patients with newly diagnosed, supratentorial glioblastoma following maximal debulking surgery and completion of radiation therapy together with concomitant standard of care chemotherapy.

e) Rationale for Conducting the Clinical Trial

Glioblastoma is the most common and deadly of the primary brain cancers in adults with a prevalence of 50,000 patients currently living with the disease²¹. Despite aggressive treatment with maximal surgical resection, radiotherapy and temozolomide, overall survival for most patients is limited on average to 14.6 months from diagnosis²². Tumor treating fields (TTFields) is a novel therapy that was initially approved by the FDA for recurrent glioblastoma in place of standard medical therapy in 2011 based on the results of an open-label phase III trial (EF-11) showing comparable survival to physician's choice chemotherapy²³. Subsequently, another open-label phase III trial (EF-14)²⁴ showed a survival benefit of adding TTFields therapy to adjuvant temozolomide chemotherapy after standard chemoradiation. The mature data was presented recently²⁵; the group that received maintenance TTFields therapy in addition to temozolomide had a median overall survival (OS) from diagnosis of 24.5 months compared to 19.8 months with temozolomide alone; 2-year OS rates were 42.5% and 30% respectively. This effect was statistically significant and irrespective of MGMT methylation status, age, extent of resection, or performance status. Investigators have demonstrated the mechanism of TTFields' antineoplastic effect involving disruption of microtubule polymerization and formation of mitotic spindles, leading to mitotic catastrophe, aneuploidy, and subsequent cell death.²⁶ However, TTFields also appears to induce apoptosis via activation of multiple immunogenic molecular pathways.²⁷ Given the apparent improvement in survival using this device in newly

diagnosed patients with glioblastoma post radiation and the potential synergy with radiation in preclinical studies, this study aims to investigate the safety and tolerability of using the TTField therapy concurrent with chemoradiation.

